5.4.2 Demographics and Baseline Characteristics Analysis

Demographic and baseline characteristics will be described descriptively. For continuous (including age, height, weight, and maximum Esophageal Eosinophil Count), means, standard deviations, medians, and ranges and for categorical (including race, ethnicity, medical history) frequency counts and percentages.

All individual subject demographic and baseline characteristic data will be listed.

5.4.3 Efficacy Analysis

The efficacy analysis will focus on changes from baseline measure to follow-up measures.

5.4.3.1 Primary Efficacy Analysis

The primary statistical efficacy endpoint will be tested using a Paired T-test on the change in peak eosinophil counts on esophageal biopsies between 1st and 2nd endoscopy after food introduction in the same patient.

If peak eosinophil counts do not satisfy the assumption of normality, instead the Wilcoxon Signed-Rank test will be used for the primary.

5.4.3.2 Descriptive analysis

Descriptive statistics will be presented by time point, and changes from baseline. Tables will use means, standard deviations, medians, and ranges for continuous variables and frequency counts and percentages for the categorical variables. Graphs will use box plots for continuous variables, and barplots for categorical variables.

All individual subject data will be listed.

Biostatistical core of Westat will help with the analysis.

5.4.3.3 Univariate testing

For measures with multiple time points, Paired statistical tests will be used with Baseline being compared to the other time points. Specifically, the statistical method will be the most appropriate of paired T-test, Wilcoxon Sign-Rank, or McNemar's tests.

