3.1.1 Disease Control

At the initial phase, research subjects will start on dupilumab based on the dosage used in the 2 phase 3 clinical trials. Based on previous data, patients respond within 12 weeks, therefore, a baseline endoscopy showing a clinical and histologic response will be obtained at week 12. If patients show clinical response with dupilumab as defined as esophagus biopsy with less than 6 eosinophils/hpf. If the biopsy does not improve such that eosinophil count is still greater than 15 eosinophils/hpf, the subject will exit the study. If the biopsy is between 6-15 eosinophils/hpf, the subject will be treated for an additional 12 weeks on dupilumab. If the biopsy is still not less than six eosinophils/hpf, the subject will exit the study. If the subjects have biopsy have less than six eosinophils/hpf (FDA definition of remission), the subjects will advance to food introduction phase of the study.

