5.3.2 Secondary Endpoints

Secondary endpoints will include the following:

- Maintenance of resolution (<15 eosinophils/HPF on peak measurements) of eosinophilia observed on esophageal biopsies
- Maintenance of remission (<6 eosinophils/HPF on peak measurements)
- Change in mean esophageal eosinophil count from baseline to the end of treatment.
- Change in symptoms scores at the end of treatment compared to baseline
- Interval change on a validated endoscopic scoring system, EREFS
- Interval change on esophageal compliance and distensibility measured by EndoFlip
- Interval change in mRNA transcriptome profile (esophageal tissue), Th2 phenotype (peripheral blood), blood eosinophilia
- Change in the Eosinophilic Esophagitis Quality of Life Score from baseline to the end of treatment

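### Both maintenance endpoints start at 100% by selection, so McNemar's test against the pre-food baseline cannot show that remission was maintained

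*Combined protocol and SAP*

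**What the plan says.** Section 5.3.2 lists two binary secondary endpoints: "Maintenance of resolution (<15 eosinophils/HPF on peak measurements) of eosinophilia observed on esophageal biopsies", and "Maintenance of remission (<6 eosinophils/HPF on peak measurements").

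Section 5.4.3.3 covers every measure with several time points: "Paired statistical tests will be used with Baseline being compared to the other time points". On the choice of test it says that "the statistical method will be the most appropriate of paired T-test, Wilcoxon Sign-Rank, or" McNemar's test. It does not define baseline, does not say which version of McNemar's test is meant, and plans no confidence interval. Section 5.4.3.4 adds a GEE model with baseline as the reference category, its distribution to be chosen from the data.

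Entry to the food phase is set in section 3.1.1: "If the subjects have biopsy have less than six eosinophils/hpf (FDA definition of remission), the subjects will advance to food introduction phase of the study". A subject at 6 to 15 at week 12 is treated for 12 more weeks and exits if the count is still not below 6. Table 1 shows no endoscopy at Visit 1, so the only in-study histology before food is the week-12 biopsy or its repeat. The synopsis has a different entry rule: it bars only counts above 15 and also asks for reduced symptoms.

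Section 5.4.3.2 provides counts and percentages by time point. Section 5.5 gives all of the alpha to the primary endpoint and calls other testing exploratory.

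**The concern.** The study asks whether trigger foods can return to the diet without a flare, and the two maintenance proportions answer that most directly. McNemar's test compares subjects who changed in one direction with subjects who changed in the other. If every subject is below 6 when food starts, nobody can change from not in remission to in remission. One of the two cells that the test compares is empty by design, and the null hypothesis reduces to a loss rate of zero.

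A non-significant result is then weak evidence of anything. In a trial that hopes to see no worsening, it is easily written up as remission having been maintained.

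**Working it through.** **Inputs.** Section 5.6 plans 19 evaluable subjects out of 30, and 30 × 0.64 = 19.2, so that figure reproduces. Section 5.6 also uses a sample size of 20, so both are carried. The plan states no figure for the maintenance endpoints. The numbers of losses below are illustrations.

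**The test with an empty gain cell.** Let k be the number of subjects who lose the status and 0 the number who gain it.

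- Exact, two-sided: p = 2 × 0.5^k
- Mid-p: p = 2 × 0.5^k − 0.5^k = 0.5^k
- Uncorrected: chi-square = k on 1 df
- Continuity-corrected: chi-square = (k − 1)²/k on 1 df

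For k = 5 these give 2 × 0.03125 = 0.0625; 0.03125; chi-square 5; and chi-square 16/5 = 3.2.

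| Losses of 19 | Exact p | Continuity-corrected p | Uncorrected p | Mid-p | Maintained (Clopper-Pearson 95% CI) |
|---|---|---|---|---|---|
| 4 (21.1%) | 0.125 | 0.134 | 0.046 | 0.063 | 15/19 = 78.9% (54.4% to 93.9%) |
| 5 (26.3%) | 0.063 | 0.074 | 0.025 | 0.031 | 14/19 = 73.7% (48.8% to 90.9%) |
| 6 (31.6%) | 0.031 | 0.041 | 0.014 | 0.016 | 13/19 = 68.4% (43.4% to 87.4%) |

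In terms of loss, 5/19 has an exact 95% interval of 9.1% to 51.2%. The same data count as a significant loss under two versions of the test and not under the other two.

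**Chance of detecting a one-quarter loss.** The exact test needs k ≥ 6 and the uncorrected test k ≥ 4. With k binomial and a true loss of 25%:

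- Exact: P(k ≥ 6) = 33% at n = 19 and 38% at n = 20.
- Uncorrected: P(k ≥ 4) = 74% at n = 19 and 78% at n = 20.

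**The GEE.** Assume a binomial logit model, 19/19 at baseline and 14/19 later. The baseline log-odds are infinite, so the model separates. A trial fit with an independence working correlation gave a time coefficient of about −24.5 with a standard error of about 540, which cannot be used.

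**If the synopsis entry rule applied.** Subjects at 6 to 15 could start food, and some could later fall below 6. Five losses and one such gain give exact p = 0.22 and uncorrected p = 0.10. The gain offsets a loss in the test, although that subject had no remission to maintain. The endpoint of below 15 would still run in one direction only, except for a subject with a count of exactly 15.

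**The case against.** Several points on the other side stand.

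- A reader might infer that everyone is below 6 at week 12. Section 3.1.1 does not say so. Subjects at 6 to 15 can enter after 12 more weeks, and that section calls the week-12 endoscopy the baseline. If week 12 is baseline for all, changes on the below-6 endpoint can go both ways. The argument is strict only against the last biopsy before food, and only under the entry rule of section 3.1.1.
- A reader might infer that the plan would call a one-quarter loss not significant. It might, or it might not: the answer depends on a version of the test that the plan leaves open.
- McNemar is not assigned to these endpoints by name. A statistician could decide that no listed paired test is appropriate and report the percentage alone. The assignment is an inference from McNemar being the only listed test for binary data.
- A reader might infer that losses would be hidden. They would not be, because section 5.4.3.2 tabulates the percentages and individual data are listed. Also, a loss of half the subjects is the upper confidence limit at 5 losses, not what was observed.
- That the p-value ignores the number of unchanged pairs is a property of McNemar's test in general, not a special fault here.

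None of this makes the test informative about maintenance. Allowing gains does not help either, since maintenance has meaning only for subjects who already had the status.

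**Conclusion.** The point holds in a limited form. Measured from the last pre-food biopsy under section 3.1.1, both maintenance endpoints begin at 100% by selection. McNemar's test then addresses only a zero loss rate, and a baseline-referenced logit GEE cannot be estimated. At 5 losses of 19, p ranges from 0.025 to 0.074 according to an unnamed version, while the data are compatible with a loss of 9% to 51%.

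This rests on three assumptions: McNemar would be used for these endpoints, baseline means the last biopsy before food, and about 19 or 20 subjects start food. The stronger inference, that the trial's main conclusion is unsafe because of this, is not supported. The primary test is a separate paired comparison, and these endpoints are exploratory. The harm is a possible misleading statement of no significant loss.

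**What to change.** In sections 5.4.3.3 and 5.4.3.4, exclude the two maintenance endpoints from McNemar's test and from the baseline-referenced GEE. Put in their place:

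- Baseline for these endpoints is the last biopsy before food introduction.
- The denominator is all subjects who start food. The all-enrolled population of section 5.4.1 includes subjects who never reach that phase.
- Report the proportion maintained with its Clopper-Pearson 95% interval at week 25 and week 51. The week-38 endoscopy is conditional under section 3.1, so it is not available for everyone. State which endoscopies correspond for a subject whose food start was delayed by the additional 12 weeks.
- Count a missing biopsy as not maintained, with an observed-case analysis as sensitivity.

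The entry rules in the synopsis and section 3.1.1 must also be reconciled, since they decide who is at risk of losing the below-6 status.

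The cost is a few sentences, with no new data, visits or procedures. The downside is a wide interval, for example 14/19 = 74% (95% CI 49% to 91%). With no reference proportion in the plan, it gives an estimate and not a pass or fail, which suits an exploratory pilot.

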5.4.3.4 Statistical Modeling

Modeling using categorical time points as the explanatory variable will be conducted with baseline as the reference category. The model will be estimated using generalized estimating equations with a covariance structure assumed for time points from the same subject. The appropriate distribution and covariance structure will be selected based on the data.

5.4.3.5 Operationalization of Variables

Distribution of the continuous outcomes will be evaluated using density and histograms. Transformation and categorization of some of these continuous variables will be performed wherever deemed more appropriate.

Re-categorization of categorical variables will be considered when appropriate.

5.4.3.6 Eosinophilic Esophagitis Symptom Score

Improvement in symptom scores will be defined as a decrease in total symptom scores of two or

more from baseline to end of treatment. Subjects will be categorized based on whether they improved their symptoms. Subjects who improved their symptom scores were considered as responders and patients who did not improve their symptom scores were considered as non-responders.

The responses will be divided into three categories as suggested: Poor <30% improvement, good 30-70% improvement and excellent >70% improvement from baseline.

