3 INVESTIGATIONAL PLAN

3.1 General Schema of Study Design

This study is an open label exploratory study to examine if patients controlled with dupilumab can successfully introduce EoE trigger foods back into their diet.

In the initial 12-week period, patients will start on dupilumab on the doses used in the phase 3 trials to control disease. If disease is controlled based on histologic and symptom control at week 12 endoscopy, patients will start on EoE trigger food. The trigger foods will be based on both a combination of history and histology results. The food will have triggered EoE by histology in the last 2 years and symptoms in the last year when reintroduced into the diet. The study will focus on the four most common foods that trigger EoE: milk, egg, wheat, and soy. For the initial food introduction, the subjects will add one serving size of the food daily for 12 weeks. After 12 weeks, the subjects will have a 2nd endoscopy if the 2nd endoscopy is normal, the subjects will increase the trigger food to 2 serving sizes a day or add an additional trigger food. A 3rd endoscopy will be done if the patients increase the food amount or adds a new food at week 38 (12 weeks after adding the new food). If the subject does not increase or add new foods at week 25, the 3rd endoscopy will not be obtained. All subjects will have end of study endoscopy at week 51.

If the subjects have abnormal endoscopy or increase in symptoms, the amount of food will be reduced by 50% and repeat endoscopy will be obtained at the same time schedule-12 weeks later. (See Figure 1 and Table 1)

Screening Phase

Potential subjects will be screened using the protocol inclusion and exclusion criteria based on review of their medical records.

Parental/guardian permission (informed consent) and, if applicable, child assent, will be obtained prior to any study related procedures being performed. After consent is obtained, research blood samples will be drawn to confirm eligibility based on clinical laboratory parameters. Females of child bearing potential will have an urine pregnancy test.

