7.10.2.3 Risks from food introduction

The main risk from food introduction is exacerbation of Eosinophilic Esophagitis symptoms. Subjects will be monitored one week by phone for increasing symptoms and study visits for worsening symptoms by validated EoE questionnaires. In addition, the other risk is worsening esophageal histology and possible long-term fibrosis with untreated disease. Therefore, we monitor for worsening disease at 12 weeks after food introduction by upper endoscopy with biopsy.

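### Symptom and QOL change is planned only against an undefined baseline, so no prespecified comparison isolates the effect of food, and the symptom categories have no class for worsening

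*Combined protocol and SAP*

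**What the plan says.** The synopsis objective is to allow trigger foods without histological or symptomatic flares, and section 2.1 asks about symptom and QOL change once food has been introduced. Section 7.10.2.3 states: "The main risk from food introduction is exacerbation of Eosinophilic Esophagitis symptoms".

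The planned analyses use a different reference:

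- Section 5.3.2 lists "Change in symptoms scores at the end of treatment compared to baseline" and "Change in the Eosinophilic Esophagitis Quality of Life Score from baseline to the end of treatment".
- Section 5.4.3.3 pairs baseline with each other time point. Section 5.4.3.4 makes baseline the GEE reference category.
- Section 5.4.3.6: "Improvement in symptom scores will be defined as a decrease in total symptom scores of two or" more points, from baseline to end of treatment; "patients who did not improve their symptom scores were considered as non-responders". The bands are "Poor <30% improvement, good 30-70% improvement and excellent >70% improvement from baseline". The section does not say whether PEESS or PESQ is scored; both are collected.

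Section 4.1.1 labels Visit 1 the baseline visit, and the first dupilumab dose is given there. Section 3.1.1 calls the week 12 endoscopy a baseline endoscopy. Section 5.3.2 also measures mean eosinophil count from baseline, yet Table 1 has no endoscopy before Visit 4. The analysis section does not define the term.

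On food, section 3.1 says: "If the subjects have abnormal endoscopy or increase in symptoms, the amount of food will be reduced by 50" percent. On analysis choices, section 5.4.3.5 says: "Transformation and categorization of some of these continuous variables will be performed wherever deemed more appropriate".

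**The concern.** Food starts only after about 12 weeks of dupilumab. If symptom and QOL change is measured from the first-dose visit, improvement during the run-in can offset deterioration on food, and the net figure may look favourable in a patient whose symptoms returned. The documents lead one to expect a sizeable run-in response: 39 of 41 patients (95%) in the site's own retrospective series improved clinically on dupilumab (section 1.3.1.1), and the synopsis requires decreased symptoms before food is started.

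At stake is the symptomatic half of the objective, since the primary test covers eosinophil counts only. Without a fixed contrast, instrument and threshold, these could be chosen after open-label data have been seen.

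**Working it through.** The plan gives no sample size, score range or threshold rationale for symptoms or QOL, so it has no figure of its own to reproduce here. The scores below are illustrative.

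**Decomposition.** End − Visit 1 = (week 12 − Visit 1) + (end − week 12). The first bracket is the run-in on drug and the second is the food period. The objective concerns the second; the plan estimates the sum.

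**Section 5.4.3.6 with Visit 1 as baseline.**

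| Visit 1 / week 12 / end | Change on food | Visit 1 to end | Two-point rule | Band |
|---|---|---|---|---|
| 20 / 5 / 5 | 0 | −15 (75%) | responder | excellent |
| 20 / 5 / 14 | +9 | −6 (30%) | responder | good |
| 20 / 5 / 18 | +13 | −2 (10%) | responder | poor |
| 20 / 5 / 5, with 15 at week 25 | +10 at week 25, 0 at end | −15 (75%) | responder | excellent |

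- *Responder label.* Let B be the Visit 1 score and D the run-in fall. The patient stays a responder if end ≤ B − 2. The pre-food score is B − D, so the largest hidden rise is (B − 2) − (B − D) = D − 2. That is 3, 8 and 13 points for D = 5, 10 and 15.
- *Bands.* Staying at least *good* needs end ≤ 0.7B, so the largest hidden rise is 0.7B − (B − D) = D − 0.3B. At B = 20 this is D − 6: 9 points for D = 15 and 4 for D = 10. For D = 5 the patient is already *poor* (25%) before food.
- *A flare that settles.* In the last row the score rises by 10 and returns to 5, as could happen if food is reduced under section 3.1. Neither the label nor the band shows it, because both use only the final score.

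**The same rule with week 12 as baseline.** 20/5/5 changes by 0, so the patient is a non-responder. 20/5/18 changes by +13, also a non-responder. Improvements of 0% and (5 − 18)/5 = −260% are both below 30%, so both are *poor*. Stable and worse are pooled.

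**Group-level illustration.** Assumptions: 19 subjects, Visit 1 mean 40 and SD 12, error SD 6 or 10, 20,000 simulated trials per setting. Ranges cover the two error SDs.

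| Run-in fall, true rise on food | Still responder | Still *good* or better | Visit 1 test significant for improvement | Week 12 test significant for worsening |
|---|---|---|---|---|
| 60%, 12 points | 73–82% | 49–50% | 87–99% | >99% |
| 40%, 6 points | 70–79% | 41–44% | 78–99% | 73–99% |
| 40%, 12 points | 55–58% | 17–28% | 19–39% | >99% |

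Masking is strong when the run-in fall is large relative to the later rise, and weak otherwise.

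**Precision of a pre-food contrast.** Section 5.6 gives 30 × 0.64 = 19.2, hence 19 evaluable subjects. A two-sided paired t-test at 0.05 then has 80% power for a change of 0.68 SD of the paired difference. A proportion of 15/19 (79%) has an exact 95% CI of 54% to 94%; for 19/19 the lower limit is 82%.

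**The case against.** The strongest reply is that the trial will still show symptomatic flares, and much of it stands.

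- A reader might infer that section 5.4.3.6 cannot tell 20/5/18 from 20/5/5. It can: both are responders, but the bands grade them *poor* and *excellent*. The D − 2 result applies to the responder label alone.
- A reader might infer that worsening is captured nowhere. That is true only of section 5.4.3.6. Section 5.4.3.2 plans by-visit summaries and individual listings. Section 7.3 counts any unfavourable symptom as an adverse event, section 7.10.1 monitors visits for worsening EoE symptoms on food, and section 5.4.5 summarizes adverse events by time period. A clinically recognised flare, even one that settles, should appear there. This is not a score-based comparison with the pre-food state, however.
- The section 5.4.3.4 model can yield a week 12 contrast. It can, but none is prespecified, and section 5.4.3.5 leaves categorization open.
- Baseline might mean week 12. Visit 1 is the more natural reading for symptoms and QOL, but the documents do not settle it. The week 12 reading removes run-in masking but leaves stable and worsened patients in one class.
- Section 5.5 makes these tests exploratory. That lowers the severity; it does not supply the missing comparison.

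**Conclusion.** The concern holds in a limited form. Symptom and QOL change is referenced only to a baseline that the analysis section does not define. If that is Visit 1, the planned estimates mix the drug run-in with the food effect and do not answer the symptomatic part of the objective or the aim in section 2.1. On either reading, section 5.4.3.6 has no worsened category.

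At Visit 1 and week 12 scores of 20 and 5, a post-food rise of up to 13 points leaves the responder label unchanged, and a rise of up to 9 still ends as *good*. These sizes follow from the plan's own cut-offs applied to assumed scores; the simulated rates rest on assumed distributions as well.

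Two stronger conclusions are not supported: that flares would go unseen in the trial, and that the primary result is compromised. The listings and safety summaries answer the first, and the primary test uses eosinophil counts, not symptom scores. Severity is low to moderate.

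**What to change.** 1. Define baseline for each endpoint. Keep the Visit 1 comparison for symptoms and QOL, labelled as net change.
2. Add a prespecified exploratory contrast, paired or from the GEE model, with 95% CI, for one named symptom instrument and for QOL. It should run from the last pre-food assessment (normally Visit 4) to the first post-food endoscopy visit (normally Visit 8) and to end of treatment. The Visit 8 comparison matters because a flare may settle before the end.
3. Among all who took a first serving, report the proportion whose symptom score worsened from the pre-food score at those visits, with an exact CI. Fix and justify the threshold before analysis; the documents give no basis for the two points.
4. Reconcile the passages that determine which assessment is pre-food and how exposure to food changes: food start (Table 1 at Visit 4 against sections 3.1.2 and 4.2.1 at week 13/Visit 5), entry to the food phase (synopsis against section 3.1.1), and the trigger for reducing food (section 3.1 against section 3.1.2).

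The cost is SAP text and the choice of instrument and threshold. Sections 4.1.4 and 4.2.4 already collect symptoms and QOL at Visits 4, 8, 12 and 16. For subjects given the additional 12-week run-in (section 3.1.1), Table 1 shows no separate visit, so their pre-food assessment needs confirming. The downside is one more exploratory contrast of low precision.
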